15.2 METHOD OF PRIMARY ANALYSIS

The analyses that will be conducted are similar to those described in Section 9.3. For the analysis of change in HRQoL between baseline and week 24, an analysis of covariance will be conducted to compare treatment groups. The outcome of this model is change in cognitive function. Treatment group assignment will be included in the model as a predictor, and the baseline measure of HRQoL function will be included as a covariate.

A linear random coefficient model stratified by drop-out pattern will assess whether HRQoL changes over time are consistent across treatment groups and drop-out patterns. This pattern-mixture model accounts for within subject correlation of longitudinal assessments.

If assumption for conducting these analyses fail, alternative analytic approaches will be considered include, a transformation of the outcome data, or nonparametric methods.

Given the number of HRQoL tests that will be conducted, p-values will be adjusted for multiple comparisons.

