Secondary	To assess radiographic response in newly diagnosed HGG patients treated with standard RT and TMZ in combination with BMX-001 compared to standard RT and TMZ alone.	Proportion of subjects with complete or partial radiographic response.	See Section 16.5.2
Secondary	To characterize the repeated-dose pharmacokinetic profile of BMX-001 when delivered in combination with RT and TMZ in newly diagnosed HGG patients.	Plasma concentrations and calculated pharmacokinetic parameters (maximum concentration, time to reach maximum concentration, area under the curve, half-life, total body clearance, and volume of distribution) will be determined for BMX-001.	See Section 16.5.2
Exploratory	To describe patient-reported outcomes of HRQoL in newly diagnosed HGG patients treated with standard RT and TMZ in combination with BMX-001 compared to standard RT and TMZ alone.	Mean change from baseline at each follow-up assessment for subscales of the following PROs include Functional Assessment of Cancer Therapy-Brain Cancer (FACT-BR) version 4, Functional Assessment of Cancer Therapy- Fatigue (FACIT-Fatigue) subscale, version 4, Functional Assessment of Cancer Therapy- Cognition (FACT-Cog) subscale, Beck depression inventory (BDI-II), revised version, Godin Leisure questionnaire.	See Section 16.5.3

Exploratory	To describe changes in hair loss in newly diagnosed HGG patients treated with standard RT and TMZ in combination with BMX-001 compared to standard RT and TMZ alone.	Subjective investigator and patient assessment, photographs.	See Section 16.5.3
Exploratory	To describe change in white matter integrity in newly diagnosed HGG patients treated with standard RT and TMZ in combination with BMX- 001 compared to standard RT and TMZ alone.	MRI Brain Diffusion Tensor /Susceptibility Imaging (white matter integrity).	See Section 16.5.3

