9.3 METHOD OF ANALYSIS

For the analysis of change in cognition between baseline and week 24, an analysis of covariance (ANCOVA) will be conducted to compare treatment groups within the treated patient cohort. The outcome of this model is change in cognitive function. Treatment group assignment will be included in the model as a predictor, and the baseline measure of cognitive function will be included as a covariate.

As noted earlier, a significant amount of the follow-up cognitive assessments may be missing due to health decline, disease progression, and death. Much of the missing data is due to a subject permanently dropping out of the longitudinal assessment. A linear random coefficient model stratified by drop-out pattern will assess whether cognitive changes over time are consistent across treatment groups and drop-out patterns. This pattern-mixture model accounts for within subject correlation of longitudinal assessments.

If assumption for conducting either the ANCOVA model or the pattern mixture model are not satisfied, alternative approaches to analyses may be conducted. Options include transformation of the outcome data, as well as use of nonparametric methods.

Given that numerous endpoints will be examined that relate to cognition, adjustments for multiple comparisons (e.g., false discovery rate methods or Bonferroni) may be considered.

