15.1 ENDPOINT

Though the study is a longitudinal analysis, the initial focus of the analyses of this objective is an examination of the mean change in HRQoL between baseline and week 24 (occurs after completion of RT) within each treatment arm of the treated subjects.

There is variability in the timing of follow-up measurements. For the purpose of this analysis a +/- 4 week window will define the 24 week assessment.

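### SAP 15.2 contradicts itself on the HRQoL ANCOVA: it introduces a model of HRQoL change, then names change in cognitive function as the outcome

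*SAP*

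**What the plan says.** SAP 15.2 sets out how the arms will be compared on health-related quality of life, the first exploratory objective. It opens by pointing to the cognition section: "The analyses that will be conducted are similar to those described in Section 9.3". It then introduces the week-24 comparison: "For the analysis of change in HRQoL between baseline and week 24, an analysis of covariance will be conducted to compare treatment groups". The next sentence defines the dependent variable: "The outcome of this model is change in cognitive function". The one after that makes treatment group a predictor and says that "the baseline measure of HRQoL function will be included as a covariate".

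A second model follows in the same section, a random-coefficient model stratified by drop-out pattern. It "will assess whether HRQoL changes over time are consistent across treatment groups and drop-out patterns".

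The endpoint itself is given in SAP 15.1 as "an examination of the mean change in HRQoL between baseline and week 24", by arm among treated subjects. Protocol Table 2 gives the HRQoL endpoint as "Mean change from baseline at each follow-up assessment for subscales of the following PROs", followed by the list of instruments.

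**The concern.** The sentence at issue is part of the model definition, not background. It names a dependent variable from another objective, so the ANCOVA has one outcome in its introduction, a different one in its definition, and a baseline covariate that fits only the first.

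At stake is whether the week-24 ANCOVA estimates an effect on HRQoL at all. Someone who programmed from the outcome sentence alone would regress a cognitive change score on arm and baseline HRQoL. The trial is also open-label, so a correction made after results are known could look like a choice made in the light of them.

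**Working it through.** The SAP gives no sample size, power or alpha for HRQoL, so there is no figure to reproduce. The check is mainly a comparison of texts.

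**1. Outcome and covariate, place by place**

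| Place | Outcome | Baseline covariate |
|---|---|---|
| SAP 9.3 (cognition ANCOVA) | change in cognitive function | "the baseline measure of cognitive function will be included as a covariate" |
| SAP 15.1 (HRQoL endpoint) | change in HRQoL to week 24 | not applicable |
| SAP 15.2, sentence introducing the ANCOVA | change in HRQoL to week 24 | not yet stated |
| SAP 15.2, sentence defining the outcome | change in cognitive function | HRQoL (next sentence) |
| SAP 15.2, pattern-mixture model | HRQoL changes over time | not stated |
| Protocol Table 2 | mean change from baseline on PRO subscales | not stated |

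Only one entry for HRQoL is out of line. It repeats the SAP 9.3 sentence word for word. In 9.3 outcome and covariate agree; in 15.2 the covariate was adapted to HRQoL and the outcome was not.

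**2. Does any other text specify this model correctly?** No. Protocol 16.5.3.1 refers to Protocol 13.8.5 for the HRQoL methods, but 13.8.5 lists instruments and timing and no model. SAP section 3 says the SAP prevails where methods differ substantially. SAP 15.2 is therefore the only specification of the HRQoL ANCOVA.

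**3. What each version estimates.** Write C for a cognitive score, Q for an HRQoL score, and 0 and 24 for baseline and week 24.

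- Outcome sentence read literally: C24 − C0 = a + b·arm + c·Q0 + error. Here b is an arm effect on cognition.
- Evident intent: Q24 − Q0 = a + b·arm + c·Q0 + error. Here b is an arm effect on HRQoL.

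**4. Illustration on assumed values.** A simulation used 52 and 42 patients (the week-24 cognition counts in SAP 9.4.2, borrowed because none are given for HRQoL). It assumed a true HRQoL effect of 0.6 SD, no effect on cognition, a baseline to follow-up correlation of 0.5, two-sided tests at 5%, and 4,000 simulated trials per row.

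| Assumed cognition–HRQoL correlation | Literal model rejects | Intended model rejects |
|---|---|---|
| 0 | 0.047 | 0.909 |
| 0.3 | 0.049 | 0.902 |
| 0.6 | 0.052 | 0.894 |

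The literal model rejects at about its type I error rate. That follows by construction from assuming no cognition effect. It shows what the sentence would test if followed, not how likely it is to be followed.

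**5. How many models.** SAP section 15 lists 5 FACT-Br subscales, 1 FACIT-Fatigue scale, 4 FACT-Cog subscales, BDI-II and Godin: 5 + 1 + 4 + 1 + 1 = 12. This is a count of listed scores; the SAP does not say how many ANCOVAs will be fitted. Protocol Appendix H notes that FACT-Br also yields an overall score.

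**The case against.** The strongest reply is that nobody would be misled. The sentence immediately before names change in HRQoL. The endpoint section says the same, the covariate is HRQoL, the pattern-mixture paragraph speaks of HRQoL, and the closing sentence on multiplicity refers to HRQoL tests. The section is headed HRQoL. On this view the phrase is a drafting slip and not a chosen analysis. Most of that stands, and it is why the point is minor. It does not make the sentence right: it is the one that defines the model's outcome, and nothing elsewhere corrects it.

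A second reply is that the phrase could mean FACT-Cog, which measures perceived cognition and belongs to the HRQoL battery. That does not work. It would cover 4 of the 12 listed scores and leave the other 5 + 1 + 1 + 1 = 8 with no stated outcome. It would also clash with SAP section 9, where cognition means the BAC App, HVLT-R, TMT and COWA.

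A reader might go further the other way and infer that the analysis will be programmed wrongly, or that the HRQoL objective will go unanswered. The documents support neither. Misprogramming requires following one sentence against its neighbour and against 15.1. The objective is to describe patient-reported outcomes; the mean changes by arm and the pattern-mixture comparison are correctly specified and would remain even if the ANCOVA were run literally.

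**Conclusion.** The contradiction in SAP 15.2 is real, and the outcome sentence is wrong as written. Taken literally, it defines an ANCOVA that does not test HRQoL and whose baseline covariate does not match its outcome. The intended outcome is recoverable from the surrounding text, so this is an internal inconsistency and not a mistaken choice of method.

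Its reach is limited to the week-24 ANCOVA for an exploratory objective. No primary or secondary inference, sample size or error rate is affected, and neither are the pattern-mixture model and the descriptive summaries. It is worth correcting but of low severity.

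The conclusion assumes that cognitive function carries the same meaning in 15.2 as in section 9. That the sentence was carried over from 9.3 is an inference from identical wording, and the conclusion does not depend on it. Nor does it depend on the simulated rates.

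**What to change.** Rewrite the outcome sentence in SAP 15.2 so that the dependent variable is the change in the HRQoL score from baseline to week 24, with the baseline value of the same scale as covariate, and say that this applies to each HRQoL scale or subscale analysed. Protocol Table 2 already frames the endpoint by subscale, so this adds no new analysis.

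The cost is one sentence. No data, sample size or trial conduct changes. The documents do not show whether the database has been locked. If it has not, amend the SAP before lock; if it has, record the correction in the clinical study report as a clarification of the specified model, so that it is not taken for a later choice.

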15.3 ADDITIONAL ANALYSES

Additional analyses will explore the impact of BMX-001 on HRQoL within patient subgroups defined by WHO grade and histological subtype.

16 EXPLORATORY OBJECTIVE: HAIR LOSS

The second exploratory objectives is to describe changes in hair loss in newly diagnosed HGG patients treated with standard RT and TMZ in combination with BMX-001 compared to standard RT and TMZ alone.

Subjective assessments of hair loss were obtained by the treating provider for subjects at screening (baseline), after standard RT and TMZ finishes (within 2 to 4 weeks), and standard of care (SOC) clinic visit (approximately every 8 weeks) during adjuvant TMZ.

Qualitative assessments of hair loss depicted in longitudinal subject photographs will be conducted and summarized. Changes observed in Arm A will be compared to those observed in Arm B.

The analyses group for this exploratory objective will include all treated patients who have both assessments of their hair at baseline and at one or more follow-up assessments.

17 EXPLORATORY OBJECTIVE: WHITE MATTER INTEGRITY

The third exploratory objective is to describe change in white matter integrity in newly diagnosed HGG patients treated with standard RT and TMZ in combination with BMX-001 in comparison to standard RT and TMZ alone.

17.1 ENDPOINT

The mean change between baseline and each follow-up assessment for white matter integrity, as measured by MRI diffusion tensor/susceptibility imaging will be computed.

These images will be obtained three times during the study: on day -5 to 0, after standard RT and TMZ (within 2 to 4 weeks), and 24 weeks after the start of standard RT and TMZ (within 2 to 4 weeks).

17.2 METHODS OF ANALYSIS

Assuming normality, analysis of variance or a repeated measures analysis may be used to compare change in Arms A and B. Additional analyses will be sub-divided in terms of WHO grade and histological subtype.

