#### 13.8.10 MRI Diffusion Tensor/Susceptibility Imaging

MRI diffusion tensor/susceptibility imaging during Phase 2 involves the application of standard MRI imaging of the brain to evaluate white matter integrity. This will be done before contrast injection on subjects enrolled at clinical centers as indicated by the sponsor in Phase 2. All images will be acquired on state-of-the-art 3T scanners.

Imaging should include T1-weighted 3D imaging before and after single dose contrast agent injection as specified in the standardized brain tumor imaging protocol (BTIP,

https://www.ncbi.nlm.nih.gov/pmc/articles/PMC4588759/, Table 1). T2 and FLAIR imaging should also be performed as specified in this publication.

For susceptibility images, images will be acquired using a multi-echo 3D gradient echo sequence.

TE1	=min
TR	=60 ms
flip angle	= 12º
FOV	= 220x220 mm 
matrix size	= 256x256, 2mm slice thickness with no gaps,
	parallel imaging acceleration factor 2.

For **Siemens** scanners, use the following parameters:

For **GE scanners**, use the following parameters:

TE1	=min
TR	=45 ms
flip angle	= 12º
FOV	= 220x220 mm 
matrix size	= 256x256, 2mm slice thickness with no gaps, parallel imaging acceleration factor 2.

Obtain maximum number of echoes (at least 9). Sites should reconstruct and save both magnitude and unfiltered phase images from this sequence.

Diffusion tensor images will be acquired before contrast injection using a multi-channel head coil (at least 8-channels) and a standard single-shot EPI sequence with a parallel-imaging acceleration factor of 2. The parameters will be as follows: TE = 82 ms, TR = 8 s, FOV = 220x220 mm^2, matrix size = 128x128, slice thickness = 2 mm without gap, b-value = 1000 s/mm^2, 5 non-diffusion weighted images and 25 diffusion encoding directions. 75 slices will be acquired to cover the whole brain.

These images will be obtained three times during the study: on day -5 to 0, after standard RT and TMZ (within 2 to 4 weeks), and 24 weeks after the start of standard RT and TMZ (within 2 to 4 weeks).

Images will be cleaned of identifiers (except for the date of the scan which is needed for analysis), encrypted and transferred to the Duke Imaging center for analysis. Please see the sponsor provided Imaging Manual for specifics.

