### 16.5.3.3 Exploratory Objective #3 for Phase 2: White Matter Integrity

The mean change between baseline and each follow-up assessment for white matter integrity, as measured by MRI diffusion tensor/susceptibility imaging will be computed. Assuming normality, analysis of variance or a repeated measures analysis may be used to compare change in Arms A and B. Additional analyses will be sub-divided in terms of WHO grade and histological subtype.

#### 16.5.4 Interim Analysis for Phase 2

Interim analyses using an O'Brien-Fleming boundary will be conducted with the goal of terminating accrual early to accept or reject the null hypothesis of no difference in survival. Given the inflated type I error rate for this Phase 2 study, early termination will only be considered if it appears that the addition of BMX-001 treatment to radiation and temozolomide is decreasing survival. The interim analysis will be conducted to determine whether the addition of BMX-001 is possibly detrimental to the survival of patients.

Interim analyses for the primary endpoint (survival) will be conducted annually beginning June 2021. The decision rule for accrual suspension will be defined by the O'Brien-Fleming spending function and is dependent upon the number of deaths that will have been reported by the time of the interim analysis. If the boundary is crossed, accrual will be suspended while all other data (e.g. cognitive function data) is reviewed to determine whether accrual should be permanently terminated.

Though not part of the formal interim decision-making described above, additional interim analyses of secondary and exploratory outcomes will be conducted for multiple purposes, including assessment of data completeness and program planning. Currently, the planned time of these analyses is as follows:

Date	Planned Analysis
June 2020	Among the initial 80 patients treated, changes in platelet counts during
	radiation and temozolomide treatment and ending 2 weeks after termination of
	radiation will be examined. The consistency of these counts with AE reports will
	also be assessed.
December 2020	Among the initial 80 patients treated on the study, changes in neurocognition
	and quality of life PROs through week 24 will be examined. Patterns of data
	missingness will be assessed, including reasons for missed assessments.
June 2021	Among the initial 80 patients treated on the study, changes in neurocognition

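### SAP 17.2 allows white-matter change to be compared between arms without the baseline scan value as a covariate, although the SAP adjusts for baseline in its cognition and HRQoL analyses

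*SAP*

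**What the plan says.** SAP Section 17 sets the level of the objective: "The third exploratory objective is to describe change in white matter integrity". SAP 17.1 defines the outcome as "The mean change between baseline and each follow-up assessment for white matter integrity", measured by diffusion tensor/susceptibility MRI, with one scan before treatment and two afterwards. On method, SAP 17.2 offers two options and commits to neither: "Assuming normality, analysis of variance or a repeated measures analysis may be used to compare change in Arms A and B". Protocol 16.5.3.3 matches it: "analysis of variance or a repeated measures analysis may be used to compare change in Arms A and B". No covariate is named in either place, and neither says how baseline would enter a repeated measures model.

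The SAP handles its other continuous change endpoints differently. For cognition, SAP 9.3 specifies an ANCOVA of change in which "the baseline measure of cognitive function will be included as a covariate". For HRQoL, SAP 15.2 specifies the same model, in which "the baseline measure of HRQoL function will be included as a covariate".

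Not every patient is imaged. Protocol 13.8.10 states: "This will be done before contrast injection on subjects enrolled at clinical centers as indicated by the sponsor in Phase 2". The number of centers or patients imaged is not given.

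**The concern.** Subtracting a baseline value is not the same as adjusting for it. Subtraction fixes the slope of follow-up on baseline at 1. When the true slope is below 1, patients with high baseline values tend to fall and those with low values tend to rise. That movement adds noise to the change score, and a chance difference between arms at baseline shows up partly as an apparent difference in change. Including baseline as a covariate estimates the slope and removes both effects.

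The baseline scan is already scheduled, so adjustment needs no new data. Exploratory status does not explain the different treatment either, because HRQoL is also exploratory and is adjusted. At stake is the precision of the only direct imaging measure of whether BMX-001 protects white matter.

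**Working it through.** **Plan's own figure.** There is none to reproduce: the documents give no sample size, SD, effect size or power for this endpoint. The correlation r, the SD ratio k and the total number imaged N below are therefore assumptions, shown over a range.

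**Step 1: large samples, equal SDs.** Let σ be the SD at baseline and at follow-up. Per patient:

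- unadjusted change: variance 2(1−r)σ²
- change adjusted for baseline: residual variance (1−r²)σ²
- ratio: (1−r²) / [2(1−r)] = (1+r)/2

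The last column is the power of the adjusted analysis where the unadjusted one has 80% (two-sided 5%): Φ(2.802/√ratio − 1.960).

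| r (assumed) | 2(1−r) | 1−r² | Ratio | Fewer patients needed | Power with adjustment |
|---|---|---|---|---|---|
| 0.3 | 1.40 | 0.91 | 0.65 | 35% | 94% |
| 0.5 | 1.00 | 0.75 | 0.75 | 25% | 90% |
| 0.7 | 0.60 | 0.51 | 0.85 | 15% | 86% |
| 0.9 | 0.20 | 0.19 | 0.95 | 5% | 82% |

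**Step 2: chance imbalance.** With equal SDs, the slope of change on baseline is r−1. If the arms differ by D at baseline, the expected difference in unadjusted change is shifted by −(1−r)D. That is 0.7D, 0.5D, 0.3D and 0.1D in size for r of 0.3, 0.5, 0.7 and 0.9. Over repeated randomizations D averages zero, so this is extra variance and not systematic bias.

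**Step 3: unequal SDs.** With k = follow-up SD / baseline SD, the ratio is (1−r²)k² / (k²+1−2rk).

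| k | r=0.3 | r=0.5 | r=0.7 | r=0.9 |
|---|---|---|---|---|
| 0.8 | 0.50 | 0.57 | 0.63 | 0.61 |
| 1.0 | 0.65 | 0.75 | 0.85 | 0.95 |
| 1.25 | 0.78 | 0.89 | 0.98 | 0.95 |
| 1.5 | 0.87 | 0.96 | 1.00 | 0.78 |

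The gain ranges from about half the variance to almost nothing.

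**Step 4: small samples.** Estimating the slope costs a factor of about 1+1/(N−4), with N the total over both arms. This was checked by simulation with 4,000 trials per setting and equal SDs.

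| N | r | Ratio, formula | Ratio, simulated | Power unadjusted / adjusted |
|---|---|---|---|---|
| 20 | 0.5 | 0.80 | 0.80 | 75.0% / 84.4% |
| 20 | 0.7 | 0.90 | 0.90 | 76.8% / 80.7% |
| 20 | 0.9 | 1.01 | 1.00 | 75.4% / 74.8% |
| 40 | 0.5 | 0.77 | 0.75 | 77.4% / 87.7% |
| 40 | 0.9 | 0.98 | 0.97 | 78.0% / 79.6% |

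**Step 5: does the repeated measures option already adjust?** Not by itself. With complete data, a model of the two change scores by arm and visit gives, at each visit, the plain difference in mean change. So does a model of all three scans that leaves the arm means free at baseline. Adjustment enters only if baseline is a covariate or the arms are constrained to a common baseline mean. The plan states neither.

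**The case against.** The strongest reply is that the plan rules nothing out. SAP 17.2 is permissive, ANOVA is only one of two options, and Protocol 16.5.3 lets exploratory plans change if assumptions fail and lets other methods be used to test robustness. The objective is descriptive, it carries no power claim or decision rule, and white matter is absent from the output list in SAP Section 19. This stands as an argument about weight. It does not close the gap: a missing baseline covariate is not a failed assumption that would trigger a change of plan, and the repeated measures option does not supply the adjustment (step 5).

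The second reply is that ANCOVA is not guaranteed to be better. That is also correct. With 20 patients and r of 0.9 the advantage disappears, so a claim that change scores are always less precise would be wrong in finite samples.

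A reader might also infer three stronger points that the documents do not support:

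- **That this is the smallest arm comparison in the trial.** Center selection suggests a reduced number, but none is stated. Subgroup comparisons (SAP 8.5 and 9.5) or the optional hair photographs (Protocol 13.8.7) could involve fewer patients.
- **That scanner differences inflate the variance of all the measures.** Protocol 13.8.10 gives different repetition times for Siemens (60 ms) and GE (45 ms) for susceptibility imaging only; it gives one diffusion tensor parameter set. If a patient stays on one scanner, which the documents do not say, an additive vendor offset cancels in the change score.
- **That vendor could be added at no cost.** No section lists scanner vendor as a recorded analysis variable.

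**Conclusion.** The point holds as a minor, correctable gap. SAP 17.2 and Protocol 16.5.3.3 leave the baseline scan value out of the model, in contrast to SAP 9.3 and 15.2, and nothing in the documents explains the difference.

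With equal SDs and a reasonably large imaged sample, the cost of the omission is equivalent to about 35% of patients at r = 0.3, falling to 5% at r = 0.9. Unequal SDs move the variance ratio between about 0.50 and 1.00 over the range checked. At N = 20 and r = 0.9 there is no gain. All of these sizes rest on assumed r, k and N.

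It would go too far to say that the plan ignores baseline, since the outcome is change from baseline; that it commits to ANOVA; or that the arm comparison is biased, since randomization protects it on average. Impact is low because the endpoint is exploratory.

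**What to change.** Replace the method sentence in SAP 17.2 with:

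> Change at each follow-up scan will be compared between arms by ANCOVA, or by a mixed model over both follow-up scans, with arm and the baseline value of the same measure as covariates.

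Scanner vendor may be added for the susceptibility measures, but only if it is recorded. The number of patients imaged per arm at each scan should be reported, so that a reader can judge how much the adjustment could gain.

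The cost is one sentence, with no new scans, since the baseline value is already part of the change score. SAP Section 3 gives the SAP precedence where methods differ substantially from the protocol, so amending the SAP before database lock is enough. After lock, Section 3 would have the adjusted comparison identified in the clinical study report as an unplanned analysis.
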